# 9. RESEARCH METHODS

## 9.1. Study design

This will be a descriptive drug utilisation study using secondary data collected from databases in Sweden, Hungary, the Netherlands, and Germany. These databases will be used to identify patients who are tofacitinib users and obtain data on patient demographics, diagnoses, prescription medication dispensings, procedures, and administered screening and monitoring tests. All results will be stratified by country and approved indication (i.e., RA, PsA, and UC), unless otherwise specified. Additionally, the proportion of patients treated with tofacitinib without evidence of an approved indication will be described and tabulated, stratified by study country.

# 9.2. Setting

See Figure 1 for an overview of the study observation period, including the indexing period, the VTE Reporting Periods 1-3, and the CV and Malignancy Reporting Periods 1-3.

#### Figure 1. Overview of the study observation period

### 9.2.1. VTE Reporting Periods

A 105-month **observation period** will begin 01 April 2016 and end 31 December 2024. An 81-month **indexing period** will begin 01 April 2017 (i.e., the earliest date of the full distribution of the original aRMM materials for a country and indication [Sweden, RA]), end 31 December 2023, and be used to identify patients with  $\geq$ 1 tofacitinib prescription dispensing. Additionally, for some analyses, the indexing period will be split into the following 3 periods:

• **Reporting Period 1**, which will cover the up-to-26-month period after the initial distribution of the aRMM materials but *prior to* the PRAC/CHMP's notification of an increased risk of VTE among patients already at high risk (01 April 2017 through 31 May 2019, to allow for dissemination of DHPC letters following announcement of the provisional measures);

**Note:** Hungary will not have a **Reporting Period 1** because it received full reimbursement for RA in May 2019 and has yet to receive full reimbursement for PsA and UC (anticipated Q1 2023).

• **Reporting Period 2**, which will cover the 16-month period of and after the PRAC/CHMP's notification of an increased risk of VTE and mortality, through initial distribution and uptake of the 2019 Article 20 referral aRMM materials (1 June 2019 through 30 September 2020); and

**Note:** Hungary will not have a **Reporting Period 2** for PsA and UC because the September 2020 distribution date for the 2019 Article 20 referral aRMM materials in Hungary occurred prior to PsA and UC receiving full reimbursement (anticipated Q1 2023). Additionally, **Reporting Period 2** for RA in Hungary will only allow for <1 month of uptake of the 2019 Article 20 referral aRMM materials (which were distributed starting September 2020), in comparison to the approximate 6-7 month uptake of the

2019 Article 20 referral aRMM materials allowed for Sweden (which were distributed starting March 2020).

• **Reporting Period 3,** which will cover the 39-month period *after* the period of initial distribution and uptake of the 2019 Article 20 referral aRMM materials (1 October 2020 through 31 December 2023).

See Figure 2 for an overview of the VTE Reporting Periods 1-3.

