**Note:** Hungary will not have a **Reporting Period 2** for PsA and UC because the anticipated distribution date for the 2021 signal evaluation procedure aRMM materials (Q4 2021) will occur prior to PsA and UC receiving full reimbursement (anticipated Q1 2023). Additionally, **Reporting Period 2** for the Netherlands will be adjusted in the statistical analysis plan (SAP) to reflect distribution and uptake of the 2021 signal evaluation procedure aRMM materials in Q1 2022.

• **Reporting Period 3,** which will cover the 18-21-month period *after* the period of initial distribution and uptake of the 2021 signal evaluation procedure aRMM materials (Q2/Q3 2022 through 31 December 2023).

**Note: Reporting Period 3** for the Netherlands will be adjusted in the SAP to reflect distribution and uptake of the 2021 signal evaluation procedure aRMM materials in Q1 2022.

See Figure 3 for an overview of the CV and Malignancy Reporting Periods 1-3.

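### In Hungary RA, VTE Reporting Period 3 starts within a month of the 2019 materials going out, so nearly all of the uptake phase falls in a period defined as after uptake

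*Protocol*

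**What the plan says.** Section 9.2.1 gives each VTE period a meaning and a pair of dates. Period 2 begins with the regulators' notification and runs "through initial distribution and uptake of the 2019 Article 20 referral aRMM materials"; its dates are "1 June 2019 through 30 September 2020". Period 3 is the time after "the period of initial distribution and uptake of the 2019 Article 20 referral aRMM materials (1 October 2020 through 31 December 2023"). The dates are the same for all four countries.

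The same section, and Table 2, record "the September 2020 distribution date for the 2019 Article 20 referral aRMM materials in Hungary". A note to Period 2 then states the consequence, that this period "for RA in Hungary will only allow for <1 month of uptake of the 2019 Article 20 referral aRMM materials". The note sets this beside a figure of about 6-7 months for Sweden, where the materials went out from March 2020. No adjustment follows. Hungary has no VTE Period 1, and no VTE Period 2 for PsA or UC.

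Section 9.2.2 treats a late distributor differently. There, the second period "for the Netherlands will be adjusted in the statistical analysis plan (SAP) to reflect distribution and uptake of the 2021 signal evaluation procedure aRMM materials", because distribution in that country is expected in the first quarter of 2022, and a matching note covers Period 3.

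Sections 9.7.1.3.1 and 9.7.1.3.2 tabulate the VTE risk-factor outcomes and the outcomes in patients aged 65 and older by VTE period.

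**The concern.** The label of Period 3 promises patients who started tofacitinib once the revised materials had been distributed and absorbed. In Hungary the period opens at most 30 days after distribution began, so its first months are the uptake phase. The label is right for Sweden and Germany and wrong for Hungary.

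This matters because Hungary has so little else to show. With no Period 1, and with Period 2 for RA only, RA Period 2 against RA Period 3 is the country's only contrast by VTE period, for the VTE outcomes and for the elderly outcomes alike. Early initiators whose prescribers had barely seen the materials pull the Period 3 figure toward the Period 2 figure, so a real change would look smaller than it was.

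Period 2 also carries a different content in Hungary. It is almost entirely time before the materials. A reader who compares a Hungarian Period 2 or Period 3 figure with the Swedish figure under the same label is not comparing like with like.

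**Working it through.** **Inputs.** From section 9.2.1: Period 2 is June 2019 to September 2020, and Period 3 is October 2020 to December 2023. From Table 2, distribution of the 2019 materials: Sweden and Germany March 2020, the Netherlands May 2020, Hungary September 2020. From section 9.2.1: uptake allowance in Sweden about 6-7 months. From section 9.2.2: distribution on 1 October 2021 gives a Period 2 end of 31 March 2022, and distribution on 31 December 2021 gives 30 June 2022, so about 6 months in each case.

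**Stated figures reproduced.** Period 2: 7 months of 2019 + 9 months of 2020 = 16. Period 3: 3 + 12 + 12 + 12 = 39.

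**Uptake time inside Period 2** (distribution month to 30 September 2020, for distribution on the last or the first day of that month):
- Sweden and Germany: 184-214 days, about 6-7 months, as stated.
- The Netherlands: 123-153 days, about 4-5 months.
- Hungary: 1-30 days, under 1 month, as stated.

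**Months of Period 2 before the distribution month:**
- Sweden and Germany: 9 of 16 (56%).
- The Netherlands: 11 of 16 (69%).
- Hungary: 15 of 16 (94%).

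**Uptake months inside Hungary's Period 3**, with the Swedish allowance applied to Hungary (an assumption):
- 6 months counted from the start of September 2020 ends in February 2021: 5 of 39 = 13%.
- 6 months from the end of September, or 7 from its start, ends in March 2021: 6 of 39 = 15%.
- 7 months from the end of September ends in April 2021: 7 of 39 = 18%.

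**Effect on the contrast.** Take the middle case: uptake in September 2020 to March 2021, with 1 month in Period 2 and 6 in Period 3. Assume even accrual. Let u be the average fraction of the full change reached during uptake. The share of the true change that the Period 2 versus Period 3 contrast keeps is

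(33 + 6u)/39 − u/16 = 0.846 + 0.091u.

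- u = 0: 0.846 is kept, so 15% is lost. This is the ceiling for the middle case.
- u = 0.5 (for example, linear uptake): 0.892 is kept, so 11% is lost. For Period 3 alone the loss is 3/39 = 8%.

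**Effect of moving the boundary only**, so that Period 2 ends on 31 March 2021. Period 3 is then clean, but Period 2 has 22 months, of which 7 (32%) are uptake. The share kept is

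1 − 7u/22 = 1 − 0.318u.

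The two are equal when 0.846 + 0.091u = 1 − 0.318u, so u = 0.154/0.409, about 0.38. Above that the moved boundary does worse: at u = 0.5 it keeps 0.841 against 0.892 now.

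**Effect of three groups.** June 2019-August 2020 against April 2021-December 2023 has no uptake months on either side, so the contrast keeps the whole change whatever u is.

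**The case against.** The mismatch is disclosed. The protocol prints the under-one-month figure beside the Swedish one, and section 9.7 lets the SAP modify the plan. That stands as a reason not to call this a hidden error. It does not cure it: the dates are fixed, Hungary is named, no adjustment is announced, and section 9.2.2 announces one for the Netherlands for the same reason. Section 9.9 mentions Hungary's missing periods but not this misalignment.

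A reader might infer that Hungary's Period 2 also breaks its definition, because 94% of it precedes the materials. The document does not support that. Period 2 starts at the notification, so months before the materials belong to it everywhere, including 9 of 16 in Sweden and Germany. Hungary differs in degree, and only the start of Period 3 conflicts with the stated meaning. Nor are these months free of influence, since they all follow the notification; they are free only of the materials.

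A reader might also infer that the entire uptake phase is in Period 3, or that Hungary as a whole is affected. Up to 30 days of uptake fall in Period 2. Only RA is concerned, since PsA and UC have no Period 2 and their reimbursement is anticipated in Q1 2023.

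The size is modest for a descriptive study. If the true change were 10 percentage points (an illustration), the loss would be 10 × 0.108 = 1.1 points at u = 0.5 and 10 × 0.154 = 1.5 points at most. Table 5 gives confidence intervals 20 points wide for 97 patients and 10 points wide for 385, and Table 4 expects about 450 Hungarian patients in all. No comparative analysis is planned. This stands, and it limits the weight of the point.

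Finally, moving the boundary alone can make matters worse, as the calculation shows. That stands too, and it decides the form of the remedy.

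**Conclusion.** The point holds for Hungary RA. Period 3 begins 1-30 days after distribution began, so nearly the whole uptake phase lies in a period defined as following it: about 5-7 of 39 months, 13-18%. With even accrual and six such months, Hungary's only VTE and elderly contrast by VTE period is diluted by at most about 15%, and by about 11% if half the change is reached on average during uptake. The direction is toward no change. Period 3 is diluted, not dominated.

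This rests on two assumptions: that uptake in Hungary takes as long as the protocol allows for Sweden, and that initiations are spread evenly. The protocol does not give the number of patients indexed in those months; if initiations fall over time, the uptake share is larger. Period 2 meets its definition but serves in Hungary as the group before the materials, and it should be read as that.

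The inconsistency should be corrected because the correction is cheap, not because it threatens the study.

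**What to change.** For Hungary RA, tabulate the VTE risk-factor outcomes and the elderly outcomes stratified by VTE period in three groups:
- June 2019-August 2020: after the notification, before the materials.
- September 2020-March 2021: distribution and uptake.
- April 2021-December 2023: after uptake.

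Use the first and third groups for the before-and-after description. Do not simply move the boundary between Periods 2 and 3.

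A lighter alternative is to keep the common dates, add this split as a sensitivity tabulation, and state the misalignment in section 9.9.

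For consistency, apply the same allowance to the Netherlands' VTE boundary, where distribution in May 2020 leaves 4-5 months of uptake. The Netherlands has a Period 1, so its before group is unaffected.

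The cost is one extra Hungarian stratum, an after group of 33 months instead of 39, and boundary dates that differ between countries. Section 9.7.1 rules out pooling across countries, so no pooled result changes.

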In May 2019, the EC requested a reassessment of the benefit-risk of tofacitinib pursuant to Article 20 of Regulation (EC) No 726/2004 due to a signal for increased risks of pulmonary embolism and mortality arising in an ongoing Pfizer-sponsored Phase 3b/4 safety study (A3921133) designed to evaluate the risk of malignancy and major adverse cardiac events in RA patients aged 50 years and older who had at least one cardiovascular (CV) risk factor. In November 2019, the Committee on Human Medicinal Products (CHMP) concluded, based on a recommendation from the Pharmacovigilance Risk Assessment Committee (PRAC), that patients treated with tofacitinib are at increased risk of venous thromboembolism (VTE) events, both for deep venous thrombosis as well as pulmonary embolism, especially in patients with risk factors for VTE. The PRAC further concluded that the risk of VTE events is dose-dependent. To minimise this risk, the PRAC recommended that warnings be added to the Summary of Product Characteristics (SmPC) regarding the increased risk of VTE observed in patients taking tofacitinib, especially for patients with known risk factors for VTE. The PRAC also recommended that treatment with tofacitinib be discontinued in patients with suspected VTE and that tofacitinib 10 mg BID for maintenance treatment is not recommended in patients with UC who have known VTE risk factors unless there is no suitable alternative treatment available. Clarifications on the posology were also added, particularly for UC patients in maintenance. Specifically, some patients (i.e., patients who failed to respond to alternative treatment options for UC such as tumour necrosis factor [TNF] inhibitor treatment) who had a reduction in response to 5 mg BID maintenance treatment may benefit from an increase in maintenance dose to 10 mg BID; for these patients, the presence of known risk factors for VTE should be considered. However, tofacitinib 10 mg BID for maintenance treatment should be used for the shortest duration possible.

The PRAC also concluded that, based on the interim analyses of Study A3921133, there is a potential increased risk of mortality. This was partly driven by an increased risk of serious infections among patients 65 years and older. As such, tofacitinib should be considered

among patients 65 years and older only if no suitable alternative treatment is available. These conclusions and revisions to the SmPC were approved by the EC on 31 January 2020.

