## Figure 2. Overview of the VTE Reporting Periods

# 9.2.2. CV and Malignancy Reporting Periods

A 105-month **observation period** will begin 01 April 2016 and end 31 December 2024. An 81-month **indexing period** will begin 01 April 2017 (i.e., the earliest date of the full distribution of the original aRMM materials for a country and indication [Sweden, RA]), end 31 December 2023, and be used to identify patients with  $\geq$ 1 tofacitinib prescription dispensing. Additionally, for some analyses, the indexing period will be split into the following 3 periods:

• **Reporting Period 1**, which will cover the up-to-51-month period after the initial distribution of the aRMM materials but *prior to* the PRAC/CHMP's notification of an increased risk of CV-related outcomes and malignancy-related outcomes among patients already at high risk (01 April 2017 through 30 June 2021, to allow for dissemination of DHPC letters);

**Note:** Hungary will not have a **Reporting Period 1** for PsA and UC because it has yet to receive full reimbursement for PsA and UC (anticipated Q1 2023).

The anticipated start date of distribution of the 2021 signal evaluation procedure aRMM materials for most countries is some time in Q4 2021. Therefore, ranges have been included

for the start and end dates of the CV and Malignancy Reporting Periods 2 and 3 assuming that the 2021 signal evaluation procedure aRMM materials are distributed at the beginning of Q4 (01 Oct 2021) and at the end of Q4 (31 Dec 2021). Thus, the CV and Malignancy Reporting Period 2 will start 01 July 2021 and end either as early as 31 March 2022 (lasting 9 months) or as late as 30 June 2022 (lasting 12 months). Accordingly, the CV and Malignancy Reporting Period 3 will start either as early as 01 April 2022 or as late as 01 July 2022 and end 31 December 2023, lasting either 21 months or 18 months, respectively.

• **Reporting Period 2**, which will cover the 9-12 month period of and after the PRAC/CHMP's notification of restrictions on use in the context of increased risk of CV-related outcomes and malignancy-related outcomes, through initial distribution and uptake of the 2021 signal evaluation procedure aRMM materials (01 July 2021 through Q1/Q2 2022);

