### 9.7.1.3.2. Use in the elderly (patients aged 65 years and older)

The proportion of patients initiating tofacitinib aged 65 years and older at the index date without prior alternative therapy (defined as  $\geq 1$  biologic in the 12 months prior to index date) will be described and tabulated for VTE Reporting Period 1, VTE Reporting Period 2, VTE Reporting Period 3,vv CV and Malignancy Reporting Period 1, CV and Malignancy Reporting Period 2, and CV and Malignancy Reporting Period 3.ww Proportions will be presented overall and stratified by approved indication.

The proportion of patients aged 65 years, receiving tofacitinib, who have 0 prescription dispensings of tofacitinib from the time they turn 65.5 years old through to the end of the follow-up period, will be described and tabulated for VTE Reporting Period 1, VTE Reporting Period 2, VTE Reporting Period 3,vv CV and Malignancy Reporting Period 1, CV and Malignancy Reporting Period 2, and CV and Malignancy Reporting Period 3.ww Proportions will be presented overall and stratified by approved indication.

The proportion of patients aged 65 years, receiving tofacitinib, who have  $\geq 1$  prescription dispensing of tofacitinib from the time they turn 65.5 years old through to the end of the follow-up period and no history of alternative treatments *prior to* that tofacitinib prescription dispensing, will be described and tabulated for VTE Reporting Period 1, VTE Reporting Period 2, VTE Reporting Period 3,vv CV and Malignancy Reporting Period 1, CV and Malignancy Reporting Period 3.ww Proportions will be presented overall and stratified by approved indication.

The proportion of patients aged 65 years, receiving tofacitinib, who have  $\geq 1$  prescription dispensing of tofacitinib from the time they turn 65.5 years old through to the end of the follow-up period and a history of alternative treatments *prior to* that tofacitinib prescription dispensing, will be described and tabulated for VTE Reporting Period 1, VTE Reporting Period 2, VTE Reporting Period 3,vv CV and Malignancy Reporting Period 1, CV and Malignancy Reporting Period 2, and CV and Malignancy Reporting Period 3.ww Proportions will be presented overall and stratified by approved indication.

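### The reporting periods do not isolate the 2019 and 2021 measures, and some follow-up outcomes straddle the period boundaries

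*Protocol*

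**What the plan says.** Section 9.2.1 states that "for some analyses, the indexing period will be split into the following 3 periods". For the VTE scheme these are:

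- Period 1, the 'before' period: "01 April 2017 through 31 May 2019, to allow for dissemination of DHPC letters following announcement of the provisional measures".
- Period 2, from the 2019 notification "through initial distribution and uptake of the 2019 Article 20 referral aRMM materials (1 June 2019 through 30 September 2020)".
- Period 3, after "the period of initial distribution and uptake of the 2019 Article 20 referral aRMM materials (1 October 2020 through 31 December 2023)".

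Section 9.2.2 splits the same indexing period differently. CV and Malignancy Period 1 is "01 April 2017 through 30 June 2021, to allow for dissemination of DHPC letters". Period 2 starts on 1 July 2021 and lasts 9 to 12 months. Period 3 takes the remaining 18 to 21 months.

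Section 7 describes two successive restrictions. The first followed the Article 20 referral and covered VTE risk and patients aged 65 and over: "These conclusions and revisions to the SmPC were approved by the EC on 31 January 2020". The second, from June 2021, covers patients over 65, smokers, and patients with other CV or malignancy risk factors.

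Elderly outcomes are tabulated in both schemes. Section 9.7.1.3.2 begins with "The proportion of patients initiating tofacitinib aged 65 years and older at the index date without prior alternative therapy" and lists all six periods. Sections 9.7.1.3.1 to 9.7.1.3.4 also stratify outcomes from the 12-month follow-up by reporting period: discontinuation, continuation, the outcomes on turning 65, and the average daily dose (ADD) of UC patients.

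**The concern.** Secondary objective 2 is to describe what changed after the 2019 referral and after the 2021 signal evaluation. Section 7 says the results will feed the judgement of whether the risk minimisation materials work. Section 9.9 proposes to compare patients with VTE risk factors before and after the 2019 materials, and presents before-and-after description as a strength of the study.

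That use requires each contrast to bracket one measure. VTE Period 3 contains two. The CV 'before' period, when used for elderly patients, already contains the first age restriction. Outcomes that occur up to 12 months after index may belong, in calendar time, to a later period than the one they are reported in. A real change could be diluted, or could be visible with no means of saying which measure preceded it. Section 9.9 mentions none of these points.

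**Working it through.** **Stated period lengths.** Inclusive month counts from the protocol's dates reproduce its figures.

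- Indexing period, April 2017 to December 2023: 81 months.
- VTE periods: 26 + 16 + 39 = 81.
- CV and Malignancy periods: 51 + (9 to 12) + (21 to 18) = 81.

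**VTE Period 3.** Share after the second measure = months from the chosen start to December 2023, divided by 39.

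| Counted from | Months | Share |
|---|---|---|
| 1 July 2021, start of CV Period 2 (9.2.2) | 30 | 77% |
| Distribution of 2021 materials, start of Q4 2021 | 27 | 69% |
| Distribution of 2021 materials, end of Q4 2021 | 24 | 62% |
| Start of CV Period 3, early or late | 21 or 18 | 54% or 46% |

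The patients overlap. In Table 3 the VTE risk factors include MI, malignancy, diabetes, hypertension and age over 50. MI (within coronary artery disease), diabetes and hypertension are also CV risk factors, malignancy is also a malignancy risk factor, and age 65 and over appears in both of those lists.

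**CV Period 1 for elderly outcomes.** Share = months from the chosen start to June 2021, divided by 51.

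| Counted from | Months | Share |
|---|---|---|
| 1 June 2019, start of VTE Period 2 (9.2.1) | 25 | 49% |
| After the November 2019 CHMP conclusion (Section 7) | 19 | 37% |
| After EC approval on 31 January 2020 (Section 7) | 17 | 33% |
| March 2020 distribution, Sweden and Germany (Table 2) | 16 | 31% |

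**How follow-up outcomes are filed.** The protocol does not state the rule. The periods end on 31 December 2023 because they divide the indexing period. Follow-up runs to 31 December 2024. Filing by event date would leave 2024 events with no period, so filing by index date is the only reading that gives every event one.

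**UC dose in VTE Period 1.** This check needs no accrual assumption.

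1. ADD is assessed only in Sweden and Germany (Section 9.3.4 rules out Hungary and the Netherlands).
2. In both countries the original UC materials were distributed in September 2018 (Table 2), and earlier UC index dispensings are excluded (Section 9.2.5). The earliest possible UC index date is therefore 1 September 2018.
3. Weeks 40-47 are Days 281 to 336 (Section 9.3.4). With Day 1 = 1 September 2018, Day 281 is 280 days later. September to May is 30+31+30+31+31+28+31+30+31 = 273 days, which reaches 1 June 2019. Seven more days gives 8 June 2019.
4. VTE Period 1 ends on 31 May 2019. Even for the earliest patient, Weeks 40-47 lie wholly after it.
5. Weeks 32-39 end on Day 280, at the earliest 7 June 2019, so that interval cannot finish inside Period 1 either.

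Filed by index date, the Period 1 figure for UC patients in Weeks 40-47 contains no dosing from before the notification.

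**The case against.** Several points on the other side are sound.

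- For outcomes fixed at initiation, no index date in VTE Period 1 falls after the 2019 notification, and none in CV Period 1 falls after the 2021 one. A reader might infer that the periods fail to separate before from after altogether. The documents do not support that. The failure is in isolating one measure from the other.
- Elderly outcomes are also tabulated by VTE period, which supplies a pre-2019 baseline wherever VTE Period 1 exists (not in Hungary). A CV baseline already under the 2019 restriction is also legitimate for describing change after 2021, provided it is not read as unrestricted use. The 49% is the upper end of the 33% to 49% range between EC approval and first notification.
- A reader might infer that a fall in VTE Period 3 would be credited to the wrong measure. That goes too far. Section 9.7.1 rules out comparative analyses, and VTE factors are tabulated individually, so those untouched by the 2021 restriction can be viewed apart. The supportable statement is that a change in Period 3 cannot be assigned to either measure.
- Interim report 2 covers data to December 2022. With 12 months of follow-up required, indexing there stops in December 2021, so 9 of its 15 Period 3 months precede July 2021. This softens the mixing in that report only.
- Filing by index date is inferred, is an ordinary choice for a study of initiators, and could be settled in the SAP. The period dates themselves are fixed here. Section 9.2.2 leaves open only the boundaries that depend on Q4 2021 and the Dutch adjustment.

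Converting these month shares into patient shares, or into a share of follow-up that spills over, would require even accrual. The protocol gives no accrual by period, and its Swedish annual patient counts rise from 336 to 889 to 1912 (Table 7), so such percentages are not supported.

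**Conclusion.** The point holds in this limited form. VTE Period 3 mixes two measures: 30 of 39 months (77%) follow the 2021 notification, or 46% to 69% if counted from later implementation dates. CV Period 1 is not an unrestricted baseline for elderly patients: 33% of its months follow EC approval and 49% follow the 2019 notification. All these are shares of calendar months under the protocol's general dates. Shares for a given country and indication differ where availability began later.

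The follow-up finding rests on filing by index date and on UC patients as classified by the indication rule in Table 3. A patient with a UC code who is assigned to RA or PsA could have indexed earlier. On that basis the Weeks 40-47 result is exact for UC in VTE Period 1. The protocol's limitations section should not be silent on these points.

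**What to change.** Keep the stated periods and add the following.

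1. **VTE outcomes:** split Period 3 at 30 June 2021 (9 + 30 = 39 months).
2. **Elderly outcomes:** split CV Period 1 at 31 May 2019 and 30 September 2020 (26 + 16 + 9 = 51 months), which lines it up with the VTE scheme.
3. **ADD:** tabulate by the calendar date of the 8-week interval, and extend the last period to 31 December 2024 for follow-up outcomes so that no interval is left without a period. Dispensing dates are available in both countries that report ADD.
4. **Other follow-up outcomes:** label the tables as index-date cohorts and state the straddle in Section 9.9. Filing these by event date is not dependable. German outpatient diagnoses carry only the quarter, the 31 May 2019 boundary falls mid-quarter, and Table 3 calculates age at initiation from year of birth.

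The cost is re-tabulation of the same data. Extraction was planned to start on 30 September 2022, after this protocol version. The drawback is the cell from October 2020 to June 2021, which spans only nine months and will be imprecise, or masked, in small indication-country strata. As an illustration only, a stratum at the 100-patient minimum with even accrual would put 100 × 9/81 ≈ 11 patients there, giving a 95% interval about 2 × 1.96 × √(0.25/11) ≈ 59 percentage points wide at a proportion of 50%. Retaining the stated periods alongside means no precision is lost in the planned tables.
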